4. INTRODUCTION

4.1. Brain Contusion Background

Hemorrhagic lesions following trauma to the brain, which are referred to as contusions, may cause significant long-term morbidity and mortality. Bleeding into the brain parenchyma is problematic, due not only to the mass effect of a hematoma on intracranial pressure and associated brain herniation with compression of vital neurologic centers, but also to the neurotoxicity of hemoglobin [Kurland 2012].

In addition to the initial bleed following trauma, contusions often progress in size during the acute hospitalization period, significantly worsening prognosis. The delayed progression of bleeding into the brain is known as the hemorrhagic progression of contusion (HPC), or “blossoming” [Kurland 2012]. This expansion leads not only to an increase in hematoma volume, but also to the evolution of perihematomal edema surrounding the lesion itself. Both sequelae cause significant secondary brain injury. The prognosis for patients with traumatic brain injury (TBI) is often poor, with case fatality of up to 56%, and is worse for patients with HPC [O’Neil-Pirozzi 2018; Song 2016].

Progression of contusions are largely a function of the initial contusion volume, although other factors also contribute. Use of traditional and novel anticoagulants, antiplatelet agents, coagulopathy, age, and uncontrolled hypertension are all thought to contribute to some degree and are routinely controlled as part of clinical practice. Other processes that contribute to the progression of a contusion are analogous to the dysfunction of the cerebral microvasculature. Microvascular impairment, caused primarily by endothelial cell swelling and fragmentation, worsens hematoma expansion via the ongoing extravasation of blood into the brain parenchyma. In addition to ongoing bleeding, endothelial cell breakdown also permits the formation of perihematomal edema by extravasation of endovascular fluids into the brain’s interstitium. [Kurland 2012; Park 2008].

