16.2.2.3. Analysis of the Secondary Endpoints

GOS-E at Day 180

GOS-E at Day 180 will be analyzed as a 7-category ordinal scale (1/2, 3, 4, 5, 6, 7, and 8) using ordinal logistic regression, adjusting for covariates including all the stratification factors at randomization and baseline contusion volume per the central review and baseline GCS. Multiple imputation will be used to account for missing GOS-E at Day 180.

mRS at Day 90

mRS at Day 90 will be analyzed as a 5-category ordinal scale (0/1, 2, 3, 4, and 5/6) using ordinal logistic regression, adjusting for covariates including all the stratification factors at randomization, baseline contusion volume per the central review, and baseline GCS.

Proportion of participants requiring delayed intubation

The proportion of participants requiring delayed intubation at any time between 24 hours and 96 hours post injury or LKN will be analyzed at Day 4. The analysis will compare BIIB093 (3 mg/day or 5 mg/day) and placebo groups using a binary logistic regression, adjusting for covariates including all the stratification factors at randomization and baseline contusion volume per the central review and baseline GCS.

Change in total contusion volume (hematoma plus perihematomal edema) from baseline to 24 hours

An ANCOVA model will be used to compare BIIB093 (3 mg/day or 5 mg/day) and placebo groups, adjusting for covariates including all the stratification factors at randomization, and baseline contusion volume per the central read. This endpoint will be evaluated for all participants having a scan acquired between 12 hours after the initiation of study treatment and the end of the Hour 24 Visit. Summary statistics, including by-visit number of participants with data, mean, SD, median, quartiles, and range will be provided.

CONFIDENTIAL

The information contained herein may not be used, disclosed, or published without the written consent of
Biogen MA Inc.

Change in absolute hematoma volume from baseline to 24 hours

Analysis of covariance (ANCOVA) will be performed to compare the mean change from baseline between BIIB093 (3 mg/day or 5 mg/day combined) and placebo groups. This endpoint will be evaluated for all participants having a scan acquired between 12 hours after the initiation of study treatment and the end of the Hour 24 Visit. Summary statistics, including by-visit number of participants with data, mean, SD, median, quartiles, and range will be provided.

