### **3.5. Stratification Factors and Subgroup Variables**

#### **3.5.1. Stratification Factors**

The randomization will be stratified by the follow risk factors:

- Baseline contusion volume per investigator assessment of NCCT scan or site local radiologic assessment
  - > 3 to 10 mL
  - > 10 mL
- Baseline Glasgow Coma Scale (GCS)
  - 5 to 8
  - 9 to 12
  - 13 to 15
- Age
  - $\leq$  70 years old
  - > 70 years old
- Region
  - North America (United States)

- Rest of World (RoW)

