## 5. Statistical Methods for Planned Analyses

### 5.1. General Principles

Descriptive statistics will be provided for all efficacy endpoints. For continuous or numerical endpoints (change in volume, ██████████, GOS-E, etc.), number of participants with non-missing measures, mean, standard deviation (SD), median, quartiles (the 25th percentile or Q1, and the 75th percentile or Q3), and range (min, max) will be summarized. For categorical (nominal and ordinal) endpoints (GOS-E, mRS, etc.), number of participants with non-missing measures, number and percentage (%) of participants in each category of the endpoints will be summarized.

Treatment comparisons for the primary and secondary efficacy endpoints will be evaluated using 2-sided tests at the 0.05 level of significance. Point estimates of the treatment effect and 95% 2-sided confidence intervals (CIs) will be presented. The calculation of type I error will not adjust for multiple comparisons unless otherwise specified.

If more than 10% of data is missing for any baseline covariate, that covariate will not be used in the modeling described below.

All imaging efficacy endpoints including the primary endpoint will be evaluated by randomized treatment group using the full analysis set (the mITT participants; see [Section 3.6](#)), unless otherwise specified. The analyses performed on the full analysis set will be considered as the main analyses [[ICH E9 \(R1\) Addendum, 2020](#)].

The primary and secondary efficacy endpoints will also be analyzed based on the per-protocol analysis set as supplementary analyses. ██████████

██████████ The final model for each main analysis for the full analysis set will be used for the corresponding per-protocol analysis.

Subgroup analysis will be performed for primary and secondary efficacy endpoints and will present a point estimate of the treatment effect and 95% 2-sided CIs from unadjusted analyses, i.e., without including stratification factors or other covariates in the model other than the treatment group. These analyses will be performed on the full analysis set only. If the number of participants in a subgroup is too small (e.g. < 10% of mITT participants), the analysis in that subgroup may not be performed.

The software used for this analysis plan is SAS Studio.

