### 5.6.1. General Analysis Methods for Efficacy Endpoints

All endpoint models (binary logistic regression, ordinal logistic regression, Cox model, and analysis of covariance) below will regress the outcome on the randomized treatment group, comparing the BIIB093 combined with placebo groups, adjusting for all the IRT stratification factors at randomization (see [Section 3.5.1](#)), baseline contusion volume per the central review and baseline GCS.

Analysis of covariance (ANCOVA) will be performed to compare the change in total contusion volume (primary analysis), change in absolute hematoma volume, the change in absolute edema volume, [REDACTED] from baseline in the main analysis comparing the BIIB093 combined with placebo groups. The least square (LS) mean difference with the corresponding 2-sided 95% CI and p-values for the treatment group will be provided.

Binary logistic regression will be used for binary outcomes comparing the BIIB093 combined with placebo groups. Odds ratio, the corresponding 2-sided 95% confidence interval (CI) and p-value will be reported for the treatment group.

Ordinal logistic regression (proportional odds model) will be used for GOS-E as a 7-category ordinal scale (1/2, 3, 4, 5, 6, 7, 8) and for mRS as a 5-category ordinal scale (0/1, 2, 3, 4, 5/6) at Day 90 and 180. Odds ratio, the corresponding 2-sided 95% CI and p-value for the treatment group will be reported.

The proportional odds ratio assumption will be tested using likelihood ratio test based on observed data. In the case the assumption does not hold (p-value < 0.05) or non-convergence, the Mann-Whitney test will be used as the primary inference and the source of non-proportionality or non-convergence will be investigated. Following the Mann-Whitney test, dichotomized analysis will be conducted to assess the treatment effects.

The Cox proportional hazard model will be used to assess the treatment effect on overall survival at Day 90 for all randomized participants. Hazard ratio, 2-sided 95% CI as well as the p-value for the treatment group will be reported. Kaplan-Meier curves will be presented by randomized treatment group, and Greenwood's formula will be used to calculate the standard error of the Kaplan-Meier estimates.

Multiplicity will be not be adjusted for the tests of the primary and secondary endpoints, since the current study sample size is not powered for a moderate treatment effect on GOS-E.

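### SAP 5.6.1's fallback primary test for GOS-E and mRS is a Mann-Whitney test with no stated stratification and no matched estimate; a rank test stratified by GCS and contusion volume would be a cheap improvement

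*SAP*

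**What the plan says.** SAP 5.6.1 analyses GOS-E (7 categories) and mRS (5 categories) by proportional-odds regression. The covariates come from this sentence: "All endpoint models (binary logistic regression, ordinal logistic regression, Cox model, and analysis of covariance) below will regress the outcome" on randomised group, with the IRT factors, centrally read baseline volume and baseline GCS. The list names four regression methods and no rank test. For the ordinal model, "Odds ratio, the corresponding 2-sided 95% CI and p-value for the treatment group will be reported".

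The switching rule follows: "The proportional odds ratio assumption will be tested using likelihood ratio test based on observed data". Then: "In the case the assumption does not hold (p-value < 0.05) or non-convergence, the Mann-Whitney test will be used as the primary inference". The next sentence adds a dichotomized analysis to assess the treatment effect. SAP 5.6.3 makes the GOS-E and mRS dichotomies covariate-adjusted logistic regressions, and 5.6.1 requires an odds ratio and 95% CI for binary outcomes.

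Related text:
- SAP 5.1, for primary and secondary endpoints: "Point estimates of the treatment effect and 95% 2-sided confidence intervals (CIs) will be presented".
- SAP 3.5.1: "The randomization will be stratified by the follow risk factors", namely volume (2 levels), GCS (3), age (2) and region (2).
- SAP Table 3 gives GOS-E at Day 180 multiple imputation. Section 5.1.4 sets 100 imputations and 5.6.3 combines them by Rubin's rule. There is no imputation for mRS (5.1.5).
- Protocol 16.2.2.3 plans both endpoints "using ordinal logistic regression, adjusting for covariates including all the stratification factors at randomization" and mentions no fallback. Protocol 16 leaves final detail to the SAP.

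**The concern.** When the check fires, the primary p-value moves from an analysis that uses the baseline factors to one that, as written, ignores them. Under stratified randomisation the arms are balanced on those factors. The Mann-Whitney null variance still counts the spread between strata as noise, so if the strata predict outcome the test rejects too rarely.

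Three details are also open.
- No effect measure belongs to the rank test. The dichotomized odds ratio addresses one cut-point, and the common odds ratio comes from the model just set aside.
- Rubin's rule needs an estimate and a standard error. The SAP names neither for the rank test and does not say whether the fallback uses observed or imputed data.
- It is not stated whether the likelihood ratio test covers the treatment term or every term.

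At stake are two Phase 2 secondary endpoints, and only in trials where the switch fires.

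**Working it through.** **1. The plan's own figure.** The only power figure is for the primary endpoint: 80 per pooled group, difference 15 mL, SD 29 mL. 15 / (29 × √(2/80)) = 15 / 4.585 = 3.27; 3.27 − 1.96 = 1.31, so power is 90.5% (90.2% with the t distribution). The stated 90% reproduces. No power figure is given for GOS-E, mRS or the fallback.

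**2. Scope of the proportionality check.** With K categories, freeing one column costs K − 2 degrees of freedom: 5 for GOS-E and 3 for mRS. If the model has eight columns (treatment, volume stratum, two GCS dummies, age, region, central volume, GCS), freeing all of them costs 40 and 24. These are different triggers under one sentence.

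**3. The tests.** In stratum s let m be the number on BIIB093, k on placebo, n = m + k, and R the BIIB093 rank sum with midranks. Van Elteren: Z = Σ[R − m(n+1)/2]/(n+1) ÷ √Σ[V/(n+1)²], where V = (mk/12)·[(n+1) − Σ(t³−t)/(n(n−1))] and t is the number tied in each category. Mann-Whitney is the same with one stratum. Since R − m(n+1)/2 = mk(θ − ½), where θ is the probability of the higher score with ties counted half, the matched estimate is Σwθ/Σw with w = mk/(n+1). For mRS the scale is reversed so that θ means the better outcome.

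**4. Single-test power at an odds ratio of 2.** The documents give no outcome distribution or covariate strength, so both simulations assume them. Both use permuted blocks of 4 within the 24 strata and no missing data.
- Simulation A: 150 patients, 2,500 trials per cell (SE at most 1.0 point). GCS bands 30/25/45%. Log-odds effects weak/moderate/strong: GCS per SD 0.4/0.8/1.3, log volume per SD 0.2/0.4/0.7, age over 70 0.3/0.7/1.1.
- Simulation B: 160 patients, 1,500 trials per cell (SE about 1.2 points). GCS bands 25/25/50%. Log-odds effects GCS 5–8 −1.2, GCS 9–12 −0.6, volume above 10 mL −0.6, age over 70 −0.9, residual volume −0.3 per SD, all times a multiplier.

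| Case | Mann-Whitney | van Elteren, 6 strata | Adjusted model | Gain |
|---|---|---|---|---|
| A, GOS-E none | 66 | 66 | 68 | 0 |
| A, GOS-E weak | 64 | 66 | 68 | +2 |
| A, GOS-E moderate | 55 | 63 | 67 | +8 |
| A, GOS-E strong | 39 | 57 | 65 | +18 |
| A, mRS moderate | 52 | 60 | 65 | +8 |
| A, mRS strong | 34 | 51 | 60 | +17 |
| B, GOS-E ×0 | 70.9 | 69.4 | 71.3 | −1.5 |
| B, GOS-E ×0.5 | 67.5 | 67.5 | 70.8 | 0.0 |
| B, GOS-E ×1 | 59.2 | 62.9 | 70.1 | +3.7 |
| B, GOS-E ×1.5 | 52.2 | 61.3 | 70.2 | +9.1 |
| B, mRS ×1 | 57.4 | 60.8 | 66.9 | +3.4 |
| B, mRS ×1.5 | 47.1 | 53.7 | 62.3 | +6.6 |

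In B at ×1 and ×1.5 the stratified test recovers 3.7/10.9 = 34% and 9.1/18.0 = 51% of the GOS-E gap to the adjusted model. Using all 24 strata does worse than six in B (GOS-E 65.4, 63.9, 61.9 and 60.4% across the multipliers).

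**5. Type I error, nominal 5%.** A: Mann-Whitney alone 1.8–3.6%, van Elteren 4.1–5.0%, full SAP rule 5.1–5.6%. B (GOS-E, ×1 and ×1.5): Mann-Whitney 4.2 and 2.9%, van Elteren 4.4 and 4.8%.

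**6. Power of the whole rule (A, check on the treatment term).** With proportional odds and moderate covariates the switch fires in 5–6% of trials. Replacing the fallback moves power from 66.2 to 66.8% (GOS-E) and from 63.8 to 64.2% (mRS).

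With benefit concentrated at one end of the scale (assumed cut-point odds ratios 3.5 down to 1.1 for GOS-E, 3.2 down to 1.1 for mRS, or reversed), gain ≈ P(switch) × power difference among switched trials. Moderate covariates:

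| Case | P(switch) × difference | Simulated rule |
|---|---|---|
| GOS-E low end | 0.29 × (45 − 36) = 2.6 | 45.9 to 48.5 (+2.6) |
| GOS-E high end | 0.41 × (59 − 52) = 2.9 | 58.5 to 61.3 (+2.8) |
| mRS low end | 0.36 × (40 − 32) = 2.9 | 41.9 to 44.6 (+2.7) |
| mRS high end | 0.53 × (55 − 50) = 2.7 | 55.2 to 58.2 (+3.0) |

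Strong covariates: +3.1 and +5.2 (GOS-E), +4.3 and +5.4 (mRS). No covariate effect: −0.5 to +0.3.

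**The case against.** A reader might infer that the fallback leaves the endpoint with no effect estimate at all. The documents do not support that: the sentence after the switching rule adds the dichotomized analysis, and 5.6.3 makes it covariate-adjusted with an odds ratio and CI. What stands is narrower: no estimate is matched to the rank test that carries the primary p-value.

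A reader might also infer that the fallback is always the weakest choice, or that it inflates type I error. Neither holds. With weak or absent covariate effects the two rank tests are close, or Mann-Whitney is slightly ahead. Mann-Whitney errs on the conservative side, and the full rule stays at 5.1–5.6%.

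The remaining objections have weight.
- Prognostic strength for GOS-E and mRS is assumed. Protocol 4.1 says "Progression of contusions are largely a function of the initial contusion volume", but that concerns imaging progression, and the SAP's reference to risk factors names no outcome or size.
- The whole-rule figures take the check as limited to the treatment term, which the SAP does not say. How often its own rule would fire is therefore unknown.
- Neither simulation includes missing data, so the pooled version over imputations is untested.
- The adjusted proportional-odds model beat the stratified rank test wherever there was a treatment effect. Keeping it as primary, with proportionality as a diagnostic, is a legitimate alternative close to Protocol 16.2.2.3. Under real non-proportionality, however, its odds ratio is only an average.

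These points limit the size of the gain. They do not supply a reason to leave the fallback unstratified.

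**Conclusion.** The point holds as a cheap improvement. The fallback has no stated stratification in a trial that randomises by the relevant factors, and it has no estimate of its own. If GCS and volume are moderately to strongly prognostic, stratifying on them gains about 3 to 9 points of single-test power in simulation B (8 to 18 in A) and brings a conservative test closer to its nominal level. Over the whole rule the benefit is modest: under 1 point with proportional odds and moderate covariates, about 3 to 5 points with the non-proportional effects assumed here. All of this rests on assumed covariate strengths and outcome distributions. If the strata are not prognostic, about 0 to 3 points are lost. A reader might extend the point to the trial's main result; that does not follow, because the primary endpoint is analysed by ANCOVA and the fallback applies only to two secondary endpoints, and only when triggered.

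**What to change.** In SAP 5.6.1:
1. Replace the Mann-Whitney test by the van Elteren test stratified by IRT GCS category and IRT contusion-volume category (six strata, weights 1/(n+1)).
2. Report with it the stratified probability of a better outcome on BIIB093 (ties count half) and its 95% CI, with weights mk/(n+1) so that it matches the test. Name the variance method.
3. For GOS-E, pool over the imputations by applying Rubin's rule to that estimate and its standard error.
4. Limit the likelihood ratio test to the treatment term (5 df for GOS-E, 3 df for mRS) and keep the p < 0.05 trigger.
5. State that the non-convergence trigger refers to the proportional-odds model, not to the less constrained model fitted for the check.

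The cost is SAP wording and some programming. No patients, visits or data are added, since the strata are already in IRT. The price is the 0 to 3 points of power at risk if the strata do not predict outcome.

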Change in absolute edema volume from baseline to 96 hours

ANCOVA will be performed to compare the mean change from baseline between BIIB093 (3 mg/day or 5 mg/day) and placebo groups. This endpoint will be evaluated for all participants having a scan acquired between 12 hours after the initiation of study treatment and the Hour 96 Visit. Multiple imputation will be used to account for missing values for the Hour 96. Summary statistics, including by-visit number of participants with data, mean, SD, median, quartiles, and range will be provided.

Time to all-cause death, including neurological death, through Day 90

Survival time will be analyzed for all randomized participants. Cox proportional hazards regression models will be used to assess the treatment effects on overall survival at Day 90 after adjusting for covariates including the stratification factors at randomization, baseline contusion volume per the central review, and baseline GCS. Kaplan-Meier curves will be presented for BIIB093 (3 mg/day or 5 mg/day) and placebo groups.

CONFIDENTIAL

The information contained herein may not be used, disclosed, or published without the written consent of Biogen MA Inc.

[REDACTED]

[REDACTED]

[REDACTED]

[REDACTED]

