### **3.2.2 Actual Treatment Group**

Actual treatment refers to the actual study drug received by a participant.

- Randomized participants who are dosed but never receive any BIIB093 during study treatment administration will be assigned to placebo group.
- Randomized participants who receive any BIIB093 will be assigned to BIIB093 3 mg/day group, if the IV dose during bolus  $< 0.17$  mg and the following IV infusion received by the participant  $< 11.31$  mg for Infusion 1 and  $< 13.525$  mg for Infusion 2; refer to Table 1 of the protocol.
- Randomized participants who receive any BIIB093 will be assigned to BIIB093 5 mg/day group, if the IV dose during bolus  $\geq 0.17$  mg or the following IV infusion received by the participant  $\geq 11.31$  mg for Infusion 1 or  $\geq 13.525$  mg for Infusion 2.
- Randomized participants who never receive any study drug (neither BIIB093 nor the matching placebo) will have missing actual treatment group and will be excluded in the analysis by actual treatment group.

Study results for safety (adverse events, serious adverse events, laboratory, vital signs, liver function test, electrocardiogram [ECG]), extent of exposure, [REDACTED] will be analyzed and presented by actual treatment group.

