## 3.6. Analysis Sets

The analysis sets include the full analysis set (the modified intention-to-treat participants), per-protocol analysis set, and the safety analysis set. All participants who have signed the informed consent form will be used for the enrollment summary. All randomized participants following the intention-to-treat principle will be used for time-to-event analysis (including the participants who are randomized but do not receive any study drug).

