To explore the exposure-response relation of different BIIB093 doses, similar efficacy endpoint models will be used for analyzing the two active dose arms separately (BIIB093 3 mg/day vs. BIIB093 5 mg/day vs. placebo). The results of the exposure-response analysis will report point estimate of the treatment effect (odds ratio, hazard ratio, or least-square mean difference) and the corresponding 2-sided 95% CIs. No p-values for the exposure-response analysis will be reported.

Table 3: Main Analyses for Efficacy Endpoints

Endpoints	Analysis method	Analysis Population	SAP Section
Primary endpoint			
Change in total contusion volume as measured by brain imaging from baseline to 96 hours or prior to DC, IPH evacuation or CMO if these procedures occur before 96 hours per the central review	Analysis of Variance (ANCOVA)	mITT per-protocol	5.6.2

Secondary endpoints			
GOS-E at Day 180	Ordinal logistic regression with multiple imputation	mITT per-protocol	5.6.3
mRS as 5-category ordinal scale (0/1, 2, 3, 4, 5/6) at Day 90	Ordinal logistic regression	mITT per-protocol	5.6.3
mRS as 2-category ordinal scale (0-2 vs 3-6) at Day 90	Binary logistic regression	mITT per-protocol	5.6.3
Proportion of participants requiring delayed intubation	Binary logistic regression	mITT per-protocol	5.6.3
Change in total contusion volume from baseline to 24 hours or prior to DC, IPH evacuation or CMO if these procedures occur before 24 hours per the central review	Analysis of Variance (ANCOVA)	mITT per-protocol	5.6.3
Change in absolute hematoma volume from baseline to 24 hours	Analysis of Variance (ANCOVA)	mITT per-protocol	5.6.3
Change in absolute edema volume from baseline to 96 hours	Analysis of Variance (ANCOVA)	mITT per-protocol	5.6.3
Time to all-cause death through day 90	Cox proportional hazards regression model	mITT per-protocol	5.6.3

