### Change in Absolute Edema Volume from Baseline to 96 Hours

Change in absolute edema volume from baseline to 96 hours will be analyzed in the Day 4 database.

- ANCOVA will be performed to compare the mean change between BIIB093 combined and placebo groups based on the observed data.
- By-visit mean and change in absolute edema volume from baseline will be summarized.

[figure not shown]
## Time to All-cause Death, Including Neurological Death, through Day 90

Survival time in days through Day 90 is defined as the time from randomization to death, including all-cause death and neurological death. For a participant who discontinues and is not known to have died during the study, survival time will be censored at the time when the participant is last known to be alive of the study. Survival time will be analyzed in the Day 90 database for all randomized participants.

- Survival time will be analyzed using Cox proportional hazards regression models of overall survival after adjusting for covariates specified in Section [5.6.1](#).
- Kaplan Meier curves of survival will be presented for BIIB093 3mg/day, BIIB093 5 mg/day, BIIB093 combined and placebo groups.

A horizontal bar chart consisting of 10 black bars of increasing length from left to right. The bars are set against a white background. The first bar is the shortest, and the 10th bar is the longest, extending almost to the right edge of the frame.

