### **5.7.3 Death**

All-cause deaths and deaths by the neurological criteria will be summarized for all randomized participants.

- Number (%) of deaths during on-treatment will be summarized by actual treatment group.
- Number (%) of deaths before Discharge, Day 30, Day 90 and Day 180 will be summarized by actual treatment group.

- Listing of deaths during the study will be provided, including timing of the death relative to study treatment and the investigator assessment of the cause of death.

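### SAP Table 3 names the wrong analysis population for time to death, against the protocol and the SAP's own text

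*SAP*

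**What the plan says.** SAP 5.6.1 contains "Table 3: Main Analyses for Efficacy Endpoints". Its row "Time to all-cause death through day 90" gives a Cox model, names mITT and per-protocol in the population column, and refers the reader to SAP 5.6.3. All randomized participants are not listed in that row.

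The other statements of the population for this endpoint are:

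- Protocol 16.2.2.3: "Survival time will be analyzed for all randomized participants".
- SAP 3.6: "All randomized participants following the intention-to-treat principle will be used for time-to-event analysis". The sentence goes on to include participants who were randomized but never dosed.
- SAP 5.6.1, running text: "The Cox proportional hazard model will be used to assess the treatment effect on overall survival at Day 90 for all randomized participants".
- SAP 5.6.3, under time to all-cause death: "Survival time will be analyzed in the Day 90 database for all randomized participants".

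SAP section 6, which is the place to declare changes from the protocol's analyses, is marked not applicable.

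For descriptive death counts, SAP 5.7.3 says: "All-cause deaths and deaths by the neurological criteria will be summarized for all randomized participants". Its bullets then tabulate those deaths by actual treatment group. SAP 3.2.2 says that participants who never receive study drug "will have missing actual treatment group and will be excluded in the analysis by actual treatment group".

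**The concern.** Survival to Day 90 is a named secondary objective, tested at the two-sided 0.05 level with no multiplicity adjustment. One SAP section gives two populations for it, and the one in the summary table differs from the protocol without being declared as a change.

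The difference is not cosmetic. Membership of the mITT set (SAP 3.6.1) is settled after randomization. It needs dosing and a central read from a scan taken at least 10 hours after the infusion starts, and no later than the Hour 96 visit or earlier neurosurgery or comfort measures. A survival comparison in that set depends partly on having survived, and stayed free of those interventions, long enough to be scanned. The per-protocol set (SAP 3.6.2) also removes participants whose infusion stopped within 12 hours, and it is analyzed by actual treatment. Neither set preserves the randomized comparison for deaths. A programmer working from the table would produce a different hazard ratio and p-value from one working from the text.

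The death table has a smaller problem of the same kind: a summary for all randomized participants cannot be completed by a grouping in which some of them have no group.

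**Working it through.** **1. Stated figures.** The documents give no event count, hazard ratio or power for time to death, so there is no survival figure to reproduce. The only power figure concerns the primary endpoint: 80 against 80, difference 15 mL, SD 29 mL, two-sided 5%. It reproduces. 15 / (29 × √(2/80)) = 3.271; 3.271 − 1.960 = 1.311; Φ(1.311) = 90.5%. The t-test gives 90.2%, against about 90% stated. This point does not affect it.

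**2. The statements side by side.**

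| Place | Population for time to death |
|---|---|
| Protocol 16.2.2.3 | All randomized |
| SAP 3.6 | All randomized, including never dosed |
| SAP 5.6.1, text | All randomized |
| SAP 5.6.3 | All randomized |
| SAP 5.6.1, Table 3 | mITT and per-protocol |

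Four statements agree and one does not. The exception sits in the same section as one of the four and cites another of them. The rationale in the protocol's Version 2 amendment summary supports the four: all randomized participants were chosen so that survival data would be kept whether or not admissible images existed.

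**3. Who would be lost under the Table 3 row.** Three groups: never-dosed participants; those who die before a qualifying scan; and those whose neurosurgery or comfort measures come before one. A death after a qualifying scan stays in mITT, however early it is. Protocol 16.2.1 starts the scan window at 12 hours where SAP 3.6.1 uses 10, so the lost group also differs slightly between the documents.

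**4. Illustration of the bias (all death counts assumed).** Take 80 per arm and remove early deaths from each. With p = (deaths − removed) / (80 − removed), the apparent cumulative-hazard ratio is ln(1 − p_active) / ln(1 − p_placebo).

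| Deaths, active / placebo | Removed, active / placebo | Ratio, all randomized | Ratio after removal |
|---|---|---|---|
| 16 / 16 | 2 / 2 | 1.00 | 1.00 |
| 16 / 16 | 0 / 4 | 1.00 | 1.30 |
| 16 / 16 | 4 / 1 | 1.00 | 0.82 |
| 12 / 20 | 2 / 6 | 0.56 | 0.65 |
| 12 / 20 | 0 / 4 | 0.56 | 0.69 |

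Second row worked: p_active = 16/80 = 0.200 and p_placebo = 12/76 = 0.158; ln(0.800) / ln(0.842) = 1.30. The bias can go either way, and it vanishes in the null case when losses are equal.

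**5. Illustration of lost precision (also assumed).** Power is Φ(|ln HR| × √(D/4) − 1.960). At HR 0.6, 16, 32 or 48 deaths among 160 give 17%, 30% or 42%. If a quarter of the deaths are excluded (12, 24 or 36 left), these become 14%, 24% and 34%. Power is low either way, so bias matters more than the loss of events.

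**6. The death table.** SAP 5.7.3 takes all randomized participants as its population; SAP 3.2.2 leaves undosed participants without an actual group and drops them from tables by that group. Both cannot be met if anyone is randomized and not dosed.

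**The case against.** The strongest reply is that the table does not govern. SAP 5.6 applies mITT to efficacy endpoints only where nothing else is specified, and SAP 3.6, the 5.6.1 text and 5.6.3 do specify otherwise. Every row of Table 3 carries the same population entry, which looks like a cell copied down rather than a decision about survival. SAP 5.1 calls per-protocol analyses supplementary, so the table title overstates that set's role. A careful statistician would fit the Cox model to all randomized participants. All of this stands. A reader might infer from Table 3 that the sponsor plans to analyze survival in mITT and so discard early deaths; the documents do not support that.

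A reader might also want to state what share of deaths would be lost. The documents give no planning death rate. Protocol 4.1 cites case fatality of up to 56% in traumatic brain injury, and Protocol 4.3.2 reports no deaths in the earlier study in that condition; neither is a rate for this trial. Several features should keep losses before a scan low: the exclusions for expected withdrawal of care, herniation, immediate surgery and nonsurvivable polytrauma; dosing within an hour of randomization; and the request for a scan before surgery or comfort measures.

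On SAP 5.7.3, it would be wrong to infer that deaths in undosed participants disappear. The same section provides a listing of deaths during the study, and the all-randomized Cox and Kaplan-Meier analyses count those through Day 90. What fails is the by-group summary.

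None of this removes the contradiction. A table of main analyses is a natural source for output specifications, and it is wrong on this row.

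**Conclusion.** The Table 3 row contradicts the protocol and three statements in the SAP, one of them in its own section, and it is not a declared change. All randomized is the better-supported reading, so this is an error in the table and not a defect in the intended analysis.

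The consequence is conditional. Only if the row were followed would the hazard ratio be open to selection bias, and then only through undosed participants and those without a qualifying scan. The size and direction cannot be computed from the documents; the figures above rest on assumed counts and show only that a few uneven losses could move the estimate noticeably. The SAP 5.7.3 point holds as a narrower inconsistency in one descriptive summary. Both should be corrected, because the endpoint is a formal secondary one and the correction is simple.

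**What to change.** - **SAP Table 3, row for time to all-cause death:** change the population to all randomized (main), by randomized group. Keep per-protocol, labelled supplementary, because SAP 5.1 plans it for the secondary endpoints and deleting it would create a new conflict. If mITT is kept, label it supplementary too.
- **SAP 5.7.3:** present the all-randomized death summary by randomized treatment group. If a summary by actual group is also wanted, label it as the safety analysis set.

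The cost is SAP wording and, at most, one additional death table. Data collection and trial conduct do not change. The correction should be made before survival is analyzed by arm.
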